13.1. Adverse Events

AEs will be coded using MedDRA Version 25.0.

Treatment-emergent AEs (TEAEs), defined as those AEs occurring after the first administration of study treatment until the last study visit, will be tabulated in frequency tables by System Organ Class (SOC) and Preferred Term (PT) based on the Medical Dictionary for Regulatory Activities for treatment and follow-up periods. Missing date information will be handled using the algorithm described in [Section 8.3](#).

TEAEs during treatment period are defined as AEs with onset date on or after the first dose date till 4 weeks after the last treatment or early discontinuation date whichever is earlier. TEAEs during follow-up period are defined as AEs with onset date post treatment period (4 weeks after the last treatment or early discontinuation date, whichever is earlier) to follow-up visit date.

AEs will be summarized using the number and percent of subjects reporting each SOC and PT and sorted alphabetically by SOC and by descending frequency of PT within SOC.

Subjects who experienced multiple events within the same SOC will be counted once in the SOC summary. Subjects who experienced multiple occurrences of events with the same PT will be counted once in the PT summary.

When summarizing by causality or maximum severity, if a subject experiences more than 1 occurrence of the same AE, the occurrence with the greatest severity and the closest association with the study drug will be used in summary tables. TEAEs related to study drug/study procedure are those that are identified as reasonable possibility. If relationship or severity are missing, the event will be considered as AE related to study drug/study procedure or severe AE.

An AESI is a noteworthy treatment-emergent event for the study drug that should be monitored closely and reported promptly. An AESI can be either serious or non-serious. Based on the potential risks of Nemolizumab and the risks associated with biologics in general (i.e., class effects), the following AEs will be considered as AESIs:

- Injection-related reactions,
- Newly diagnosed asthma or worsening of asthma,
- Infections,
- Peripheral oedema: limbs, bilateral,
- Facial oedema
- Elevated ALT or AST ($> 3 \times$ ULN) in combination with elevated bilirubin ($> 2 \times$ ULN).

The following summary tables for TEAEs will be presented for all TEAEs (i.e., TEAE all causalities) and study drug related TEAEs separately by treatment period and follow-up period.

This document is confidential.

- Overall Summary of TEAEs :
 - Overall summary table includes summary of subjects reporting TEAEs,
 - Overall summary table includes summary of subjects reporting TEAEs by Country,
 - TEAE by maximum severity [Mild, Moderate, Severe],
 - TEAE related to study drug,
 - TEAE related to study drug by maximum severity [Mild, Moderate, Severe],
 - TEAE related to protocol procedure,
 - Serious TEAE,
 - Serious TEAE related to study drug,
 - Severe TEAE,
 - TEAE of special interest,
 - TEAE leading to study drug interruption,
 - TEAE leading to study drug withdrawal,
 - TEAE leading to study discontinuation,
 - TEAE leading to death,
 - TEAE related to study drug leading to death
- TEAEs by SOC and PT
- TEAEs by SOC and PT and by Country
- Serious TEAEs by SOC and PT
- TEAEs by SOC, PT and maximum severity
- Severe TEAEs by SOC and PT
- TEAEs leading to study drug withdrawal by SOC and PT
- TEAEs leading to study discontinuation by SOC and PT
- TEAEs of special interest by category by SOC and PT
- TEAEs occurred in $\geq 5\%$ of subjects by SOC and PT
- TEAEs occurred in $\geq 5\%$ of subjects by Preferred Term
- Adjudicated TEAEs by SOC and PT
- TEAEs of Asthma and AESI reported by investigator with adjudication outcome by IAC
- Confirmed adjudicated TEAEs by SOC, PT and maximum severity
- TEAEs of special interest by category, SOC, PT and maximum severity

For overall study period which includes all periods (treatment and follow-up), the following summary tables will also be presented and repeated for all TEAEs (all causalities) and study drug related TEAEs.

- Overall Summary of TEAEs

This document is confidential.

- TEAEs by SOC and PT

For the subset of subjects with COVID-19 infection, the following summary tables will be provided additionally for all TEAEs and study drug related TEAEs, separately.

- Overall summary of TEAEs
- TEAEs by SOC and PT
- Serious TEAEs, by SOC and PT
- TEAEs of Special Interest by category by SOC and PT

In addition, the exposure-adjusted incidence rate (i.e., number of subjects per 100 patient-years) will be summarized for all TEAEs (all causalities) and study drug related TEAEs during treatment period.

Exposure-adjusted incidence rates of TEAEs is defined as the number of subjects exposed to treatment and experiencing a certain event divided by the total time of all subjects who are at risk for the event. Specially, for subjects with no event the exposure time is the time from the first drug intake to the end of treatment period. Exposure years is calculated as last study drug exposure date minus first study drug exposure date plus one, divided by 365.25 which is the number of days count in a year. This exposure year calculated for each subject is then added cumulatively and is derived for each treatment arm. So each treatment arm will have one value for exposure years (also known as “patient years”). The exposure year calculation is different in case of subjects who have completed the study or discontinued from the study or having withdrawn from the study due to any reason. Only the event occurred during the treatment period will account for calculation.

Subject listings will be presented for all

- TEAEs,
- TEAEs of special interest,
- Serious TEAEs,
- Severe TEAEs,
- TEAE leading to permanent discontinuation of study drug,
- TEAEs leading to deaths,
- Pre-treatment AEs,
- Adjudicated Asthma AEs,
- TEAE comments,
- Adjudicated Asthma AE comments by Independent Adjudication Committee.

Subject listings of TEAEs for subjects with COVID-19 infection will also be generated.

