8.2. Key Definitions

Screening period is a period of up to 4 weeks before Baseline/Day 1 during which subject eligibility is evaluated. Subjects receiving rescue therapies during the screening period are not eligible to participate in the study.

The 24-week **treatment period** is defined as Baseline/Day 1 to Week 24. If early discontinued during treatment period, it is defined as the period until 4 weeks (<=28 days) after last dosing date or early termination date whichever is earlier.

Follow-up period is defined as the post end of treatment period to follow-up visit in respective treatment period.

The **Baseline value** is defined as the last non-missing value before the first dose of study drug. In case that the date of first injection is not available, the date of randomization is considered.

For diary data (PP NRS, SD NRS), the Baseline values will be derived from data collected during the 7 days prior to the first administration of study drug, if subject is treated. Otherwise, the data collected during 7 days prior to randomization will be used. Baseline score will be the weekly prorated average of non-missing subject diary scores reported during the 7 days. A minimum of 4 daily scores out of the 7 days is required to calculate the weekly prorated average score. If there are less than 4 non-missing assessments in the baseline diary window, the interval lower bound can be extended up to 7 additional days, one day at a time, to obtain the most recent 4 non-missing values. For sensitivity analysis, a minimum of 2 or 3 daily scores out of the 7 days will be used to calculate the weekly prorated average score for primary and key secondary endpoints and the interval will not be extended with additional days.

The **date of first treatment** is defined as the date of first injection of study drug.

The **date of last treatment** is defined as the date of last injection of study drug.

Study day is defined as the number of days from the date of first treatment (randomization date if not treated) and will be calculated as follows:

- If the event date \geq date of first treatment, then study day = event date - date of first treatment + 1. Treatment Day 1 is therefore defined as the day of first treatment.

This document is confidential.

- If the event date < date of first treatment, then study day = event date - date of first treatment.

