	14.3.1.1.13	Overall Summary of Treatment Emergent Adverse Events (TEAEs) of Special Interest during Follow-up Period, All Causalities	Safety Population
	14.3.1.1.14	Overall Summary of Treatment Emergent Adverse Events (TEAEs) of Special Interest during Treatment Period, Study Drug Related	Safety Population
	14.3.1.1.15	Overall Summary of Treatment Emergent Adverse Events (TEAEs) of Special Interest during Follow-up Period, Study Drug Related	Safety Population
	14.3.1.2.1	Treatment Emergent Adverse Events (TEAEs) during Treatment Period by SOC and PT, All Causalities	Safety Population
	14.3.1.2.2	Treatment Emergent Adverse Events (TEAEs) during Follow-up Period by SOC and PT, All Causalities	Safety Population
	14.3.1.2.3	Treatment Emergent Adverse Events (TEAEs) during Overall Study Period by SOC and PT, All Causalities	Safety Population

This document is confidential.

Header	Table Number	Name	Analysis Set
	14.3.1.2.4	Treatment Emergent Adverse Events (TEAEs) during Treatment Period by SOC and PT, All Causalities	Safety Population – Subjects with COVID-19 Infection
	14.3.1.2.5	Treatment Emergent Adverse Events (TEAEs) during Follow-up Period by SOC and PT, All Causalities	Safety Population – Subjects with COVID-19 Infection
	14.3.1.2.6	Treatment Emergent Adverse Events (TEAEs) during Overall Study Period by SOC and PT and by Country, All Causalities	
	14.3.1.3.1	Treatment Emergent Adverse Events (TEAEs) during Treatment Period by SOC and PT, Study Drug Related	Safety Population
	14.3.1.3.2	Treatment Emergent Adverse Events (TEAEs) during Follow-up Period by SOC and PT, Study Drug Related	Safety Population
	14.3.1.3.3	Treatment Emergent Adverse Events (TEAEs) during Overall Study Period by SOC and PT, Study Drug Related	Safety Population
	14.3.1.3.4	Treatment Emergent Adverse Events (TEAEs) during Treatment Period by SOC and PT, Study Drug Related	Safety Population – Subjects with COVID-19 Infection
	14.3.1.3.5	Treatment Emergent Adverse Events (TEAEs) during Follow-up Period by SOC and PT, Study Drug Related	Safety Population – Subjects with COVID-19 Infection
	14.3.1.4.1	Exposure-Adjusted Incidence Rate for Treatment Emergent Adverse Events (TEAEs) during Treatment Period by SOC and PT, All Causalities	Safety Population
	14.3.1.5.1	Exposure-Adjusted Incidence Rate of Treatment Emergent Adverse Events (TEAEs) during Treatment Period by SOC and PT, Study Drug Related	Safety Population

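### Section 13.1 gives conflicting person-time rules for the exposure-adjusted adverse event rate, and its only explicit formula leaves out the weeks after the last injection, in which events still count

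*SAP*

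**What the plan says.** SAP Section 13.1 (Adverse Events) defines the rate as the number of exposed subjects with a given event, "divided by the total time of all subjects who are at risk for the event". Four statements about the denominator follow or can be drawn from the text:

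- Event-free subjects: "for subjects with no event the exposure time is the time from the first drug intake to the end of treatment period".
- The calculation in years: "Exposure years is calculated as last study drug exposure date minus first study drug exposure date plus one, divided by 365.25".
- The total: "So each treatment arm will have one value for exposure years".
- An exception: "The exposure year calculation is different in case of subjects who have completed the study or discontinued from the study", extended to withdrawals for any reason. No formula is attached.

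Only events in the treatment period enter the numerator. Section 13.1 words that window this way: "AEs with onset date on or after the first dose date till 4 weeks after the last treatment or early discontinuation date whichever is earlier". Section 8.2 (Key Definitions) sets the treatment period as Day 1 to Week 24 and, after early discontinuation, says "it is defined as the period until 4 weeks (<=28 days) after last dosing date or early termination date whichever is earlier".

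The rate feeds two outputs listed in Section 18 (Index of Tables). Table 14.3.1.4.1 is titled "Exposure-Adjusted Incidence Rate for Treatment Emergent Adverse Events (TEAEs) during Treatment Period by SOC and PT, All Causalities", and Table 14.3.1.5.1 is its counterpart for drug-related events.

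**The concern.** The rules cannot all be followed. Time at risk for an event differs from one event to the next, so it cannot also be a single total per arm. Time to the end of the treatment period is not time to the last injection. The exception covers completers, discontinuers and withdrawals, which is nearly every subject, yet gives nothing to program.

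Only the last-minus-first calculation is explicit, so it is the one most likely to be coded. It has two faults that work in opposite directions:

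- The interval after the last injection (28 days, or less if the subject leaves earlier) supplies events but no person-time. This raises every rate.
- Person-time continues after a subject's first event, although a subject is counted only once. This lowers rates, and matters most for common events.

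The reported quantity is an absolute rate per 100 patient-years. Two programmers could both follow Section 13.1 and report different rates from the same data, and double programming could not settle which is right.

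The end of the window is also worded inconsistently: early termination in Section 8.2, early discontinuation in Section 13.1. Section 4.1 asks subjects who stop study drug to stay in the study and reserves the early termination visit for those who leave. If discontinuation is read as stopping the drug, the two windows can differ for the same subject.

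**Working it through.** The SAP states no patient-years or rate, so there is no figure of its own to reproduce.

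**Inputs.** The last injection is at Week 20 (Section 4.1), Day 141 (Table 4-2). Week 24 is Day 169 (Table 4-2). The event window extends 28 days past the last dose (Sections 8.2 and 13.1). Dropout is 15% (Section 4.3). As a consistency check, 141 + 28 = 169, so the two descriptions of the window agree for a subject dosed on schedule.

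**Completer, time not cut at the event.** The explicit formula gives 141 − 1 + 1 = 141 days (0.386 years). The event window is 169 − 1 + 1 = 169 days (0.463 years). The ratio is 169/141 = 1.199, and 28/169 = 16.6% of the window is left out.

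**By number of doses, with a full 28-day tail.**

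| Doses | Formula (days) | Window (days) | Ratio |
|---|---|---|---|
| 6 | 141 | 169 | 1.199 |
| 5 | 113 | 141 | 1.248 |
| 4 | 85 | 113 | 1.329 |
| 3 | 57 | 85 | 1.491 |
| 2 | 29 | 57 | 1.966 |
| 1 | 1 | 29 | 29.0 |

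**Whole arm.** Assume 15% drop out, with last doses spread evenly over doses 1 to 5 (mean Day 57).

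- Formula: 0.85 × 141 + 0.15 × 57 = 128.4 days.
- Window if dropouts leave at their last dose: 0.85 × 169 + 0.15 × 57 = 152.2 days, ratio 1.185.
- Window with a full 28-day tail: 0.85 × 169 + 0.15 × 85 = 156.4 days, ratio 1.218.

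**Against event-specific time at risk.** Assume completers only and a constant hazard. With p the proportion having the event, the formula's rate is p/141 per day and the event-specific rate is −ln(1 − p)/169. The ratio is therefore p × 169 / (141 × (−ln(1 − p))).

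| p | Ratio |
|---|---|
| 5% | 1.168 |
| 20% | 1.074 |
| 30% | 1.008 |
| 31.2% | 1.000 |
| 50% | 0.865 |

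Per 100 patient-years:

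- p = 5%: 0.05/141 × 36,525 = 12.95, against −ln(0.95)/169 × 36,525 = 11.09.
- p = 50%: 129.5 against 149.8.

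**Between arms, rare events.** Assume 10% of one arm and 25% of the other stop early, with the same spread of last doses.

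- No tail: 157.8/132.6 = 1.190 and 141/120 = 1.175. Relative distortion 1.175/1.190 = 0.987.
- Full tail: 160.6/132.6 = 1.211 and 148/120 = 1.233. Relative distortion 1.233/1.211 = 1.018.
- A harsher case, 5% against 25% all stopping after two doses with a full tail, makes a true rate ratio of 1.00 read about 0.97.

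**The case against.** The best defence is that the formula's end point, the last study drug exposure date, is not a defined term. Section 8.2 defines the date of last treatment as the last injection, and Section 13.1 does not use that term. The sentence before the formula runs exposure to the end of the treatment period, so the formula might merely convert that interval to years. The remark that the calculation differs by completion status could then point to Section 8.2, which does give separate end dates for subjects who complete and those who stop early. On that reading the window lengths agree and nothing is omitted.

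Part of this stands. The 1.20 factor depends on reading the exposure date as the injection date, and the SAP should say what it means. But the reading is strained for a drug injected at clinic visits: Section 9.6 uses the same last-minus-first-plus-one arithmetic for treatment duration, explicitly with the treatment dates. Section 13.1 also makes no reference to Section 8.2 for the differing cases. Even if the defence is accepted in full, event-specific time at risk still contradicts one total per arm, and the text does not say whether time stops at the first event.

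It is also fair to say that the reach is small. No hypothesis test or efficacy result uses these rates. Nor is event-specific time the only coherent choice: a single total per arm, matched to the event window, would remove the mismatch between events and time, though it would require rewriting the opening definition.

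**Conclusion.** The concern holds. Section 13.1 contradicts itself on the denominator, and the contradiction does not depend on how the exposure end date is read.

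If that date is the last injection, which is the natural reading, rates of rare events are too high by a factor of 1.20 in completers and about 1.19 to 1.22 in an arm with 15% dropout and evenly spread last doses. Relative to event-specific time, the excess shrinks as incidence rises and reverses above about 31%. That crossover assumes completers and a constant hazard, so it is a guide only.

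The effect is confined to the absolute rates in Tables 14.3.1.4.1 and 14.3.1.5.1. The comparison between arms is little affected under the discontinuation patterns assumed, and the crude incidence tables are untouched. This should be corrected before the tables are programmed, but it does not threaten the trial's conclusions.

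**What to change.** In Section 13.1, delete the last-minus-first formula, the sentence giving one exposure total per arm, and the sentence saying the calculation differs by completion status. Replace them with one rule that follows the section's own opening definition: for each event, count days inclusively from the first injection to the earlier of the first onset of that event and the end of the treatment period, divide by 365.25, and sum over subjects in the arm. Use the same end date to decide which events count. Reconcile the wording of that end date between Sections 8.2 and 13.1, so that it is clear whether it refers to stopping study drug or leaving the study.

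The cost is a few sentences and routine programming, with no new data. Compared with the last-minus-first reading, reported rates of infrequent events will fall and those of very common events will rise.

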13.2. Laboratory Evaluations

13.2.1. Clinical Laboratory Evaluations

The hematology laboratory analyses, clinical chemistry laboratory analyses, and urinalyses will be performed at a central laboratory. Reference ranges will be supplied by the central laboratory and used by the investigator to assess the laboratory data for clinical significance and pathological changes. Reference ranges will be provided in the laboratory manual.

This document is confidential.

The following parameters will be reported for laboratory data.

- **Hematology:** Hemoglobin, hematocrit, white blood cell (WBC) count (with differential including eosinophils), red blood cell (RBC) count, platelet count, and mean cell volume (MCV).
- **Chemistry:** Creatinine, aspartate aminotransferase (AST), alanine aminotransferase (ALT), gamma glutamyltransferase (GGT), alkaline phosphatase, lactate dehydrogenase (LDH), total bilirubin, direct bilirubin, creatinine phosphokinase ([CPK], CPK isoenzyme test will be performed only if CPK is elevated to $> 2.5 \times \text{ULN}$), albumin, total protein, uric acid, sodium, potassium, calcium, chloride, glucose, urea, total cholesterol, triglycerides, low-density lipoprotein (LDL), and high-density lipoprotein (HDL). Follicle-stimulating hormone (FSH) will be collected for postmenopausal subjects.
- **Urinalysis:** pH, glucose, ketones, blood, protein, leukocytes, nitrites, bilirubin, urobilinogen, and specific gravity.

Laboratory assessments are performed at Screening, Baseline/Day 1, Week 4, Week 8, Week 16, Week 24, Early Termination and Week 32/Follow-up.

Hematology and chemistry laboratory data (absolute values and change from Baseline) will be summarized as continuous variables by visit (Baseline and scheduled visits only). Urinalysis laboratory data will be summarized by visit (Baseline and scheduled visits only). Last post-baseline, worst post-baseline and maximum post-baseline results will also be included in the summaries and will include unscheduled visits in the derivation. Worst post-baseline value will be defined as the highest or lowest value relative to the reference range. Parameters will be presented in alphabetically order.

Shift tables will be generated using the reference ranges (Low, Normal, High and Missing) for hematology and chemistry laboratory data. The number and percentage of subjects shifting from reference ranges between Baseline and each visit (scheduled visits only) will be summarized. Last, worst and maximum post baseline values will also be included in the shift tables and will include unscheduled visits in the derivation.

Summary of the number and percentage of subjects who met criteria of potential clinically significant (CS) value will be summarized (Baseline and scheduled visits only) for hematology and chemistry laboratory data. Last, worst and maximum post-baseline results will also be included in the summaries. Potentially CS ranges are listed in [Section 21.4](#).

For statistical and graphical summaries of the laboratory tests, values below or above the limit of detection (e.g. ' < 3 ' or ' > 500 ') are substituted with the lower limit of detection minus 1% for values below the lower limit and are substituted with the upper limit of detection plus 1% for values above the upper limit (e.g. ' < 3 ' is substituted by '2.97', ' > 500 ' is substituted by '505'). In data listings, the values are shown including the $<$ or $>$ sign.

Distribution of continuous hematology and chemistry laboratory data (in particular, Aspartate Aminotransferase (AST), Alanine Aminotransferase (ALT), Alkaline Phosphatase (ALP), Total Bilirubin (BILI), Creatinine Kinase (CK) and Leukocytes (WBC)) will be displayed graphically as boxplot by treatment group for baseline and for each scheduled visits and the maximum post-Baseline (including unscheduled visits in the derivation) values.

Individual subject plots will be generated for all subjects with at least one abnormal result (outside of reference range). These plots will be provided for the chemistry laboratory parameters.

This document is confidential.

By-subject listing will be presented for all laboratory data. By-subject listing for subjects with at least one abnormal result will be provided for hematology and clinical chemistry. By-subject listing for subjects with at least one potentially CS result will be provided for hematology, clinical chemistry and urinalysis.

All laboratory data will be listed for the Safety population.

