13.3. Vital Signs

Vital signs will include pulse rate, systolic and diastolic blood pressure (after the subject has been sitting for at least 5 minutes) and body temperature.

Vital signs will be collected at the Screening visit and at Baseline/Day 1, Week 4, Week 8, Week 12, Week 16, Week 20, Week 24, Early Termination visit, and at Week 32/Follow-up.

Height and weight will be measured at Screening for all subjects. Weight assessments will be conducted at Baseline/Day 1, Week 12, Week 24 and Early Termination.

All vital signs including height and weight (absolute values and change from Baseline) will be summarized as continuous (Baseline and scheduled visits only). Last post-Baseline results (including unscheduled visits in the derivation) will also be included.

The number and percentage of subjects who met criteria of potential CS value ([Section 21.4](#)) for vital signs and weight will be summarized (Baseline and scheduled visits only). Last post-Baseline results (including unscheduled visits in the derivation) will also be included.

Distribution of pulse rate, systolic and diastolic blood pressure will be displayed graphically as boxplot by treatment group for Baseline and each scheduled visit and maximum post-Baseline (including unscheduled visits in the derivation) values.

This document is confidential.

By-subject listing of subjects with potentially CS vital signs and weight will be provided.

All vital signs results will be listed on the Safety population.

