		4.53 (60 - < 70 years old, Male)	7.71 (60 - < 70 years old, Male)	
		4.86 (60 - < 70 years old, Female)	8.28 (60 - < 70 years old, Female)	
		4.58 (\geq 70 years old, Male)	7.76 (\geq 70 years old, Male)	
		5.35 (\geq 70 years old, Female)	9.10 (\geq 70 years old, Female)	
Creatinine (umol/L)	CREAT	40 (18 - < 50 years old, Male)	110 (18 - < 50 years old, Male)	> 1.5 x ULN at post-baseline, if baseline value \leq 1.5 x ULN
		31 (18 - < 50 years old, Female)	101 (18 - < 50 years old, Female)	
		40 (50 - < 70 years old, Male)	119 (50 - < 70 years old, Male)	
		31 (50 - < 70 years old, Female)	101 (50 - < 70 years old, Female)	

This document is confidential.

Statistical Analysis Plan for Interventional Studies

Sponsor: Galderma S.A./Galderma R&D, LLC; Protocol No.: RD.06.SPR.202685

Test Parameter	Test Parameter Code	Normal Range Lower Limit (LLN)	Normal Range Upper Limit (ULN)	Potentially Clinically Significant Ranges
		40 (70 - < 80 years old, Male)	137 (70 - < 80 years old, Male)	
		31 (70 - < 80 years old, Female)	110 (70 - < 80 years old, Female)	
		40 (\geq 80 years old, Male)	145 (\geq 80 years old, Male)	
		31 (\geq 80 years old, Female)	128 (\geq 80 years old, Female)	
Creatine Kinase (U/L)	CK	39 (Male)	308 (Male)	> 2.5 x ULN at post-baseline, if baseline value \leq 2.5 x ULN
		26 (Female)	192 (Female)	
Direct Bilirubin (umol/L)	BILDIR	<2.00	7.00	> 1.5 x ULN at post-baseline, if baseline value \leq 1.5 x ULN
Gamma Glutamyl Transferase (U/L)	GGT	10 (< 59 years old, Male)	61 (< 59 years old, Male)	> 2.5 x ULN at post-baseline, if baseline value \leq 2.5 x ULN
		4 (< 59 years old, Female)	49 (< 59 years old, Female)	
		10 (\geq 59 years old, Male)	50 (\geq 59 years old, Male)	
		5 (\geq 59 years old, Female)	50 (\geq 59 years old, Female)	
Glucose (mmol/L)	GLUC	3.90	5.60	< 3 at post-baseline, if baseline value \geq 3
				> 13.9 at post-baseline, if baseline value \leq 13.9
Potassium (mmol/L)	K	3.5	5.2	< 3.5 at post-baseline, if baseline value \geq 3.5
				> 5.5 at post-baseline, if baseline value \leq 5.5
Sodium (mmol/L)	SODIUM	132 (18 – < 59 years old)	147 (18 – < 59 years old)	< 129 at post-baseline, if baseline value \geq 129
		135 (\geq 59 years old)	145 (\geq 59 years old)	> 150 at post-baseline, if baseline value \leq 150
Triglycerides (mmol/L)	TRIG	0.42 (< 20 years old, Male)	1.67 (< 20 years old, Male)	> 3.69 at post-baseline, if baseline value \leq 3.69
		0.44 (< 20 years old, Female)	1.40 (< 20 years old, Female)	

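### No minimum or any-post-baseline row is planned, so the by-arm count of subjects who ever had a low clinically significant laboratory value can miss cases; vital signs have no such count in either direction

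*SAP*

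**What the plan says.** For hematology and chemistry, section 13.2.1 of the SAP supplements the by-visit rows with subject-level rows:

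- Continuous summaries: "Last post-baseline, worst post-baseline and maximum post-baseline results will also be included in the summaries and will include unscheduled visits in the derivation".
- Shift tables: "Last, worst and maximum post baseline values will also be included in the shift tables and will include unscheduled visits in the derivation".
- PCS tables: "Last, worst and maximum post-baseline results will also be included in the summaries". This sentence, unlike the other two, does not say whether unscheduled visits enter the derivation.

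The worst value is defined once: "Worst post-baseline value will be defined as the highest or lowest value relative to the reference range". No direction per parameter, no measure of distance, and no rule for a subject who goes both low and high is given. None of the three outputs has a minimum row, and the PCS table has no row for meeting a criterion at any post-baseline time.

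Section 21.4 sets both a low and a high PCS limit for many parameters. For glucose these are "< 3 at post-baseline, if baseline value" and "> 13.9 at post-baseline, if baseline value", each conditional on baseline not already being past the limit.

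For section 13.3, the number of subjects meeting PCS criteria "for vital signs and weight will be summarized (Baseline and scheduled visits only"), with a last post-baseline row added. Table 21-3 has low as well as high criteria for pulse, systolic and diastolic pressure. The maximum post-baseline value is planned for the boxplots; a minimum is not.

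Section 13.2.1 also commits to a listing: "By-subject listing for subjects with at least one potentially CS result will be provided for hematology, clinical chemistry and urinalysis". Section 13.3 has the equivalent for vital signs and weight.

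**The concern.** A reader of a safety table wants to know how many subjects in each arm ever had a low value of concern and how many ever had a high one. By-visit rows do not answer that, because the same subject may appear in several of them. The number ever affected lies somewhere between the largest single row and the sum of the rows plus any unscheduled cases. The worst row looks as if it gives the answer for the laboratory data. Whether it does depends on how a subject with excursions in both directions is handled. Highs have a dedicated maximum row to fall back on; lows have nothing. What is at stake is the by-arm incidence of findings such as low glucose, low potassium, low leukocytes or low platelets and, for vital signs, of any criterion in either direction.

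**Working it through.** The SAP states no figure to reproduce here. The check is whether its own limits allow a low PCS value to be displaced.

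**Inputs.** Reference ranges (LLN, ULN) and PCS limits from Tables 21-1 and 21-2. Assumptions: one furthest-out value per subject, and a baseline lying between the two PCS limits.

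**Rule.** Let a = LLN − low PCS limit and b = high PCS limit − ULN. If b > a, a high value can lie further outside the range than a low PCS value and still not be PCS. It is then both the worst and the maximum value, and neither row carries a flag. Because the SAP names no distance measure, three were tried: absolute (a against b), fraction of the limit (a/LLN against b/ULN), and ratio (LLN/low limit against high limit/ULN).

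| Parameter | Range | PCS low / high | a v b | Fraction | Ratio |
|---|---|---|---|---|---|
| Glucose | 3.90–5.60 | <3 / >13.9 | 0.9 v 8.3 | 0.231 v 1.482 | 1.300 v 2.482 |
| Potassium | 3.5–5.2 | <3.5 / >5.5 | 0 v 0.3 | 0 v 0.058 | 1.000 v 1.058 |
| Leukocytes | 3.80–10.70 | <3.0 / >15.0 | 0.8 v 4.3 | 0.211 v 0.402 | 1.267 v 1.402 |
| Platelets, 18 to <60 | 140–400 | <100 / >700 | 40 v 300 | 0.286 v 0.750 | 1.400 v 1.750 |
| Platelets, ≥60 | 130–394 | <100 / >700 | 30 v 306 | 0.231 v 0.777 | 1.300 v 1.777 |
| Calcium | 2.07–2.64 | <2 / >2.9 | 0.07 v 0.26 | 0.034 v 0.098 | 1.035 v 1.098 |
| Chloride | 94–112 | <94 / >115 | 0 v 3 | 0 v 0.027 | 1.000 v 1.027 |
| Hematocrit, women | 0.34–0.48 | <0.30 / >0.6 | 0.04 v 0.12 | 0.118 v 0.250 | 1.133 v 1.250 |
| Neutrophils | 1.96–7.23 | <1.5 / >9 | 0.46 v 1.77 | 0.235 v 0.245 | **1.307 v 1.245** |
| Hematocrit, men ≥59 | 0.37–0.51 | <0.30 / >0.6 | 0.07 v 0.09 | **0.189 v 0.176** | **1.233 v 1.176** |
| Hemoglobin, men ≥59 | 125–170 | <100 / ≥200 | 25 v 30 | **0.200 v 0.176** | **1.250 v 1.176** |

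Bold marks where displacement by a non-PCS high is not possible for that measure. It is not possible on any of the three for lymphocytes, sodium, hematocrit in men <59, and hemoglobin in men <59 or in women.

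**Worked cases.**

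- Glucose 2.8 and 8.0. The low value is 3.9 − 2.8 = 1.1 below LLN; the high is 8.0 − 5.6 = 2.4 above ULN. As ratios, 3.9/2.8 = 1.39 and 8.0/5.6 = 1.43. Worst = maximum = 8.0, which is not PCS, so the 2.8 is flagged in neither row.
- Potassium 3.4 and 5.4. Distances are 0.1 and 0.2; ratios are 3.5/3.4 = 1.029 and 5.4/5.2 = 1.038. Worst = maximum = 5.4, not PCS.
- Even where displacement is possible on every measure, a particular pair may depend on the choice. Leukocytes 2.8 and 13 give distances of 1.0 and 2.3, so 13 is worst; the ratios are 1.357 and 1.215, so 2.8 is worst.

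**Other readings of the definition.** If each parameter has a fixed direction, that direction is not stated. A parameter assigned the highest value loses its lows, as there is no minimum row; one assigned the lowest keeps its highs through the maximum row. If both extremes are to be shown, nothing is masked, but the text does not say so.

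**Vital signs.** The PCS rows are Baseline, each scheduled visit, and last post-baseline. A qualifying reading at an unscheduled visit that is not the last enters no row. The boxplot maximum cannot show a low pulse or low pressure.

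**The case against.** The strongest reply is that nothing is lost from the report. A low PCS value at a scheduled visit is counted in that visit's row. Every subject with a PCS result is in a by-subject listing (14.3.4.1.1.5 for hematology, 14.3.4.1.2.5 for chemistry, 14.3.4.2.3 for vital signs and weight), abnormal hematology and chemistry results are listed too, and subjects with an abnormal chemistry result get individual plots. The last-value row also draws on unscheduled readings. All of that stands. A reader might infer that low values disappear from the report, or that the vital-sign number cannot be recovered at all; the planned listings rule out both. What listings do not supply is a tabulated incidence by arm: someone has to count it by hand.

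A second reply is that one furthest-out value is a reading, not the SAP's words. That is also fair. It is the natural reading, but a fixed direction or both extremes would fit the sentence. The reply does not clear the text, since two programmers could produce different safety counts from it.

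Third, displacement needs a low PCS value and a larger high excursion in the same subject and parameter. That is true, and it limits how often this can occur.

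**Conclusion.** The point holds as a limited defect in safety tabulation. On the one-value reading, a low PCS value can go unflagged in both the worst and maximum rows for glucose, potassium, leukocytes, platelets, calcium, chloride and women's hematocrit, on all three distance measures. For neutrophils, and for hematocrit and hemoglobin in men aged 59 or over, it depends on a measure that the SAP does not give. On the fixed-direction reading, any parameter assigned the highest value loses its lows. For vital signs, no summary table gives the number of subjects per arm who ever met a low or a high criterion, whatever the reading.

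The harm is confined to subject-level incidence by arm and to unscheduled readings that are not the last, which can be missing from every count. No efficacy analysis is touched. A reader might go further and infer that a large share of low values would be missed. The SAP gives no within-subject variability and no event rates, so no such proportion can be derived from it.

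**What to change.** 1. Section 13.2.1: replace the worst value with separate minimum and maximum post-baseline values for every parameter with limits in both directions, in the continuous summaries and shift tables.
2. Laboratory PCS tables (14.3.4.1.1.3 and 14.3.4.1.2.3): add any-post-baseline rows that state explicitly that unscheduled visits are included, counting a subject once for the low criterion and, separately, once for the high criterion.
3. Section 13.3 and Table 14.3.4.2.2: add the same any-post-baseline low and high rows.
4. Vital-sign boxplots: show the minimum post-baseline value beside the maximum.

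The cost is a few sentences and table rows, with no new data. The SAP describes its table index as tentative, so added rows fit easily. PCS counts may come out slightly less favourable, so the change is best made before unblinding.
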